3.2.1 Inclusion Criteria

Patients fulfilling the following criteria are included in the study:

- Patient has purchased warfarin (Anatomical Therapeutic Chemical classification (ATC) code B01AA03) between 01-Jan-2007 and 31-Dec-2009,
- Patient has at least one INR measurement available between 01-Jan-2007 and 31-Dec-2009, and
- Patient has a International Classification of Diseases (ICD-10 version 10) diagnosis code I48 for AF between 01-Jan-2005 and 31-Dec-2009.

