3.2.2 Exclusion Criteria

- Patients with permanent residence in Finland less than 12 months prior to index date.
- Patients with age below 18 years at index date.

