4 STATISTICAL ANALYSIS

4.1 Statistical Analysis Methods

Data management, tabulations, graphics, and statistical modeling in carried out with R language (<http://www.r-project.org>). R language is described more detailed in report "R: Regulatory

Compliance and Validation Issues: A Guidance Document for the Use of R in Regulated Clinical Trial Environments" (<http://www.r-project.org/doc/R-FDA.pdf>)

A separate statistical analysis plan (SAP) including detailed statistical analysis and outputs will be produced by EPID research prior to performing any analysis.

Study population: The study population will be described at baseline (start of follow-up) using by previous drug exposure and other covariates.

Study outcomes: All study outcomes will be summarized by drug exposure and other covariates.

Drug exposure: Drug exposure starts at date of purchase. The length of the exposure period is calculated as $DDD/dose \times 1.5$, where DDD (daily defined dose) is the total amount purchased and “dose” is the amount used daily (one for an average person). For the first purchase “dose=1” and for other purchases the “dose” is calculated from previous use by dividing the previous DDD with the time between the present and the previous purchase.

The impact of the multiplier 1.5 in the construction of drug exposure will be evaluated for the primary objectives in sensitivity analyses by using multiplier values 1.25, 1.5 and 2. We will also perform a sensitivity analysis for the primary objectives by including only those patients with at least two purchases of prescriptions within a clinically meaningful timeframe of 3 months after the index date.

INR levels: Daily INR levels are calculated:

- 1) As the previous recorded INR measurement
- 2) By linear interpolation between two consecutive INR measurements. If the gap between the measurements is more than 60 days the previous measurement is applied.

Daily INR estimates are categorized into levels: under 2.0, 2.0-3.0, over 3.0. In addition when appropriate a finer categorization is used: under 1.5, 1.5-2.0, 2.0-3.0, 3.0-4.0, 4.0-5.0, 5.0-9.0, and over 9.0. This finer categorization will be used only in the analysis of the primary objectives.

Time in therapeutic range (TTR): The INR target value for AF patients is 2.0-3.0. In addition for stroke, systemic thromboembolic events, and myocardial infarction INR target above 2.0 is considered and for bleeding events INR target under 3.0 is considered.

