4.2 Power/Sample Size

Statistical hypothesis

With regard to the stroke incidence the formal statistical hypothesis between any two groups is as follows:

$$H_0 : HR = \text{Incidence}_1 / \text{Incidence}_2 = 1$$

against the alternative,

$$H_1 : HR = \text{Incidence}_1 / \text{Incidence}_2 \neq 1$$

Where HR denotes the hazard ratio, Incidence_1 is the stroke incidence rate for example in the treatment group 1 (eg, INR level below 2.0) and Incidence_2 is the stroke incidence rate in the treatment group 2 (INR level 2.0-3.0 used as the reference group).

Similar hypotheses apply for the comparisons between the other outcomes and INR targets and the TTR levels.

Power calculations

According to Wallentin¹⁴ for AF patients using warfarin the incidence rates for “stroke and systemic embolism” vary from 1.34 to 2.06 events per 100 patient years depending on the mean TTR values in different centers. For “major bleeding” events the incidence ranges from 3.11 to 4.13 and for “total bleeding” from 16.56 to 18.96. For “total death” the incidence rates vary from 3.04 to 5.72 per 100 patient years. Thus we perform power calculations for incidence rates 1.5, 3, and 6 and consider differences from of 5 % to 50% by 5% increments or equivalently relative risks from 1.05 to 1.50.

The population size in the areas participating in the study is about 3 million. About 1.6 % of the population are warfarin users and out of these about 67% are AF patients¹⁵ resulting in a study population of size 32 000. Assuming a 3-year mean follow-up time this results in 96 000 person years. According to Helin *et al.*⁸ the proportion on INR measurements in the categories: under 2.0, 2.0-3.0, and over 3.0 are 21.7 %, 63.6 % and 14.7 % respectively. In person time this means 21000 (INR under 2.0), 61000 (INR 2.0-3.0) and 14000 (INR over 3.0) person years. The power calculations are performed for the comparisons between the INR categories 2.0–3.0 as the reference group against the INR category below 2.0. Because some of the patients may not have INR measurements available we also repeat the calculations for a 20% smaller study population size. The resulting calculations are given in Table 4.2-1.

Table 4.2-1: Power (%) for comparisons between group 1 (INR below 2.0) and group 2 (INR values 2.0-3.0 used as the reference group) for different relative risk values, incidence rates and study population sizes.

Relative risk	Incidence rate per 100 patient years		

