APPENDIX 4 COMORBIDITIES

Variable	Definition (ICD-10)
Hypertension	I10-I15
Thyreotoxicosis	E05
Cardiomyopathy	I420-I422, I429
Congestive heart failure	I50
Diabetes	E10-E14
Stroke	I63, I64, I693-I698
Transient ischemic attack*	G45
Vascular disease	I20-I25, I65-I66, I672, I70
Cancer	C00-C97, D00-D09
Pulmonary embolism	I26
Other venous thromboembolism	I80-183

ICD=International Statistical Classification of Diseases and Related Health Problems.

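### No exclusion, covariate or diagnosis code identifies prosthetic heart valve or mitral stenosis, so the INR and TTR comparisons may be confounded by an unmeasured indication

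*Protocol*

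**What the plan says.** Protocol 3.2.1 sets three entry conditions:
- on drug purchases, "Patient has purchased warfarin (Anatomical Therapeutic Chemical classification (ATC) code B01AA03) between 01-Jan-2007 and 31-Dec-2009";
- on laboratory data, "Patient has at least one INR measurement available between 01-Jan-2007 and 31-Dec-2009";
- on the indication, a "diagnosis code I48 for AF between 01-Jan-2005 and 31-Dec-2009".

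Protocol 3.2.2 has two exclusions: "Patients with permanent residence in Finland less than 12 months prior to index date" and "Patients with age below 18 years at index date". None of the five conditions depends on valve status.

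Protocol 4.1 gives one target for everyone: "The INR target value for AF patients is 2.0-3.0". The same range defines the main TTR (3.4.2, 4.1), achievement of stable target (4.1.3, exploratory objective 3) and the reference INR category in the Cox models (4.1.1). Section 4.1 adds two outcome-specific targets, above 2.0 for stroke, systemic thromboembolism and myocardial infarction, and under 3.0 for bleeding. It also adds a finer INR split for the primary objectives.

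The comorbidities in 3.4.3 and Appendix 4 cover hypertension, thyrotoxicosis, cardiomyopathy, heart failure, diabetes, stroke, TIA, vascular disease, cancer and pulmonary or venous thromboembolism. The vascular row reads "I20-I25, I65-I66, I672, I70". No row holds a code for valve disease or a valve prosthesis.

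**The concern.** A factor confounds the INR comparison if it shifts the INR a patient achieves and also changes the risk of the outcome. A valve condition could do both: the treating physician may aim at another range, and the underlying thromboembolic or bleeding risk may differ. The adjusted models in 4.1.1 cannot remove this if the variable is not among the covariates.

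Two results are exposed.
- **INR over 3.0 against 2.0-3.0 (primary objectives 1-3).** Patients with a higher intended range would be over-represented in the smallest INR stratum, and their baseline risk would be read as an effect of INR.
- **TTR.** Time deliberately spent above 3.0 would count as out of range. Such patients would tend to fall below the 60% cut, and mean TTR would be lowered. Section 1.1 says that TTR evidence bears on the reimbursement question, where 60% is the threshold.

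This is a matter for the protocol. Eligibility, covariates and code lists are fixed here, and section 3.3 says that register data are requested on the basis of the protocol. A SAP could add a valve variable only if the diagnoses had been obtained.

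**Working it through.** **The plan's own figures (4.2).** 3,000,000 × 0.016 × 0.67 = 32,160, stated as 32 000. Person-years: 32,000 × 3 = 96,000. By INR category: × 0.217 = 20,832; × 0.636 = 61,056; × 0.147 = 14,112. These match the stated 21000, 61000 and 14000. No planning figure is wrong on this point.

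**Inputs from the protocol.** 14.7% of INR measurements above 3.0 and 63.6% within 2.0-3.0, used as shares of time, as the protocol itself does.

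**Assumed inputs (not in the documents).**
- p, share of the cohort with the valve conditions: 2-5%, or 640-1,600 of 32,000
- t, their share of time above 3.0: 30-60%
- u, their share of time within 2.0-3.0: 30-50%
- k, their event rate relative to other patients, for reasons unrelated to INR: 1.5-2

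**Formulas.**
- Share of time above 3.0 that they supply: S3 = pt / [pt + (1−p) × 0.147]
- Share of reference time that they supply: S2 = pu / [pu + (1−p) × 0.636]
- Apparent HR when the true HR is 1.00: [1 + S3(k−1)] / [1 + S2(k−1)]
- Fall in mean TTR, in points: p × (63.6 − 100u)

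**Results.**

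| Case | p | t | u | k | S3 | S2 | Apparent HR | TTR fall |
|---|---|---|---|---|---|---|---|---|
| Low | 0.02 | 0.30 | 0.50 | 1.5 | 0.0060/0.1501 = 4.0% | 0.0100/0.6333 = 1.6% | 1.020/1.008 = 1.01 | 0.3 |
| Middle | 0.03 | 0.45 | 0.40 | 1.5 | 0.0135/0.1561 = 8.6% | 0.0120/0.6289 = 1.9% | 1.043/1.010 = 1.03 | 0.7 |
| Middle | 0.03 | 0.45 | 0.40 | 2 | 8.6% | 1.9% | 1.086/1.019 = 1.07 | 0.7 |
| High | 0.05 | 0.60 | 0.30 | 2 | 0.0300/0.1697 = 17.7% | 0.0150/0.6192 = 2.4% | 1.177/1.024 = 1.15 | 1.7 |

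If 5% of the cohort spent no time at all within 2.0-3.0, mean TTR would fall by 0.05 × 63.6 = 3.2 points. That is the outer limit at this prevalence.

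**Sensitivity to one input.** The protocol gives 14.7% and 63.6% for all measurements, not for patients without valve conditions. With these as whole-cohort shares, S3 = pt/0.147 and S2 = pu/0.636. The high case becomes 0.030/0.147 = 20.4% and 0.015/0.636 = 2.4%, so the apparent HR is 1.204/1.024 = 1.18. The low case stays at 1.01.

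**Is a bias of that size visible?** Table 4.2-1 covers INR below 2.0 only. For over 3.0 (14,000 person-years) against 2.0-3.0 (61,000), Schoenfeld's formula with two-sided alpha 0.05 (assumed) gives power Φ(√[d × π(1−π)] × ln HR − 1.96), with π = 14/75 and d the total number of events. At HR 1.15 and a reference rate of 6 per 100 person-years, d = 840 × 1.15 + 3,660 = 4,626 and power is 96%. At rates of 3 and 1.5 it is 75% and 46%. A purely spurious HR at the top of the range could therefore often reach significance for the commoner endpoints. At the low end it would not matter.

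**The case against.** The strongest case on the other side has several parts.

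- **The premise is outside the documents.** Nothing in the protocol says that valve patients with I48 are managed above 3.0. This stands, and it is why the point is conditional. For mitral stenosis in particular, no different intended range is shown. It would confound only if achieved INR or TTR differs in these patients as well as risk.
- **The INR models classify achieved INR.** A reader might infer that an intended high INR is analysed as poor control throughout. The documents do not support that for objectives 1-3: an INR of 3.5 is counted as 3.5 whatever was intended. The issue there is confounding. Only TTR and time to target score control.
- **The 67% figure is no evidence of prevalence.** Section 4.2 states: "About 1.6 % of the population are warfarin users and out of these about 67% are AF patients". A reader might infer that a third of the cohort has another indication. The remaining 33% are users without AF, whom the I48 criterion is meant to remove. The figure says nothing about valve conditions among AF patients.
- **There are partial safeguards.** The finer INR split can show whether an excess sits in 3.0-4.0, and under the target above 2.0 an INR over 3.0 is in target for the thromboembolic outcomes. Neither removes confounding by baseline risk. The main TTR, the under-3.0 bleeding target and time to target remain affected.
- **The data could still be obtained.** Table 3.3-1 lists Care Register ICD-10 diagnoses without restricting them to Appendix 4. So it would be too strong to say that these patients cannot be identified; the plan as written simply does not do so.
- **The objectives concern AF patients in general.** Mandatory exclusion would change the target population, so it is one option among several.

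**Conclusion.** The omission is real and complete: entry conditions, exclusions, covariates and code list contain no valve item, while one INR range serves all patients. Whether it distorts the results depends on three things that the documents do not give: how many such patients there are, how much of their time is above 3.0, and how far their risk differs. On the assumed ranges, a true HR of 1.00 for INR over 3.0 appears as about 1.01-1.15 (1.18 if the protocol's percentages are taken as whole-cohort shares), and mean TTR is lower by about 0.3-3 points. The direction assumes a higher baseline risk; a lower one would bias the HR the other way. The upper end falls within the 10-20% differences named in 4.2, although that benchmark was calculated for INR below 2.0. This supports a low-cost improvement, not a conclusion that the primary comparison is invalid. Which INR target is clinically right is not judged here.

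**What to change.** Add prosthetic heart valve (Z95.2-Z95.4) and mitral stenosis (I05.0, I05.2, I34.2) to 3.4.3 and Appendix 4, so that the codes are part of the Care Register request. Then do one of the following, stated in 4.1.1:
- adjust for or stratify by these conditions in the INR and TTR Cox models, and repeat the primary INR and TTR analyses without these patients; or
- leave them out of the primary INR and TTR models and report them as a separate stratum.

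Report the number of such patients and their INR distribution, which would replace the assumptions above with data.

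Cost: a few more codes in an extraction already planned, and slightly more analysis. Where the patients are left out, the cohort is a few per cent smaller (on the assumed prevalence) and the results apply to a narrower population.

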4.1.1 Primary Objective

Objectives 1-3: Stratified incidence rates with 95% confidence intervals (CIs) will be estimated for each primary endpoint within the strata of the exposure variables (INR levels and TTR categories) and other covariates, including history of AF prior the index date.

The crude and adjusted hazard ratio (HR) estimates with 95% CIs and P-values will be estimated separately within the INR levels and TTR categories using the conventional Cox's proportional hazards model adjusting for other covariates. For INR the category 2.0–3.0 will be used as the reference category. Similarly for TTR the category $\geq 60\%$ of time will be used as the reference category.

The objectives will be evaluated separately for the prevalent warfarin user population and the new warfarin user population. The new warfarin user population consists of those patients who initiate warfarin treatment during the follow-up (01-Jan-2007 to 31-Dec-2009).

A further sensitivity analysis will be performed where the adjusted HRs are estimated stratifying by the history of AF prior to the index date.

4.1.2 Secondary Objectives

Objective 1: Stratified incidence rates with 95% CIs will be estimated for stroke, systemic thromboembolic events, myocardial infarction, and bleeding events within the strata of the exposure variables (INR levels and TTR categories) and other covariates during the first 90 days after initiation of warfarin treatment.

The crude and adjusted hazard ratio (HR) estimates with 95% CIs and P-values will be estimated separately within the INR levels and TTR categories using the conventional Cox's proportional hazards model adjusting for other covariates, including history of AF prior the index date. For INR the category 2.0–3.0 will be used as the reference category. Similarly for TTR the category $\geq 60\%$ of time will be used as the reference category.

Objective 2: Stratified incidence rates with 95% CIs will be estimated for stroke, systemic thromboembolic events, myocardial infarction, and bleeding events within the strata of the exposure variables (INR levels and TTR categories), and time from AF diagnosis to time of initiation of warfarin treatment (categories: under 6 months, 6-12 months, over 12 months). For INR the category 2.0–3.0 will be used as the reference category. Similarly for TTR the category $\geq 60\%$ of time will be used as the reference category.

Also, time from AF diagnosis to time of initiation of warfarin treatment will be added as an additional covariate to the Cox's proportional hazards model.

Objective 3: Stratified incidence rates with 95% CIs will be estimated for stroke, systemic thromboembolic events, myocardial infarction, and bleeding events within the strata of other covariates for warfarin patients after stopping warfarin treatment. Warfarin treatment is considered ended if there is more than 2 months gap since last warfarin exposure and INR measurement. Sensitivity analysis with 1 and 3 months gaps will be performed to study the robustness of the definition.

4.1.3 Exploratory Objectives

Objective 1: Stratified incidence rates with 95% CIs will be estimated for anemia as endpoint within the strata of the exposure variables (INR levels and TTR categories) and other covariates.

The crude and adjusted hazard ratio (HR) estimates with 95% CIs and P-values will be estimated separately within the INR levels and TTR categories using the conventional Cox's proportional hazards model adjusting for other covariates. For INR the category 2.0–3.0 will be used as the reference category. Similarly for TTR the category $\geq 60\%$ of time will be used as the reference category.

Objective 2: Discontinuity period of warfarin treatment due to a surgical operation or intervention is identified as starting two weeks before and ending two weeks after such procedure.

Stratified incidence rates with 95% CIs will be estimated for stroke, systemic thromboembolic events, myocardial infarction, and bleeding events in the strata of other covariates within periods of warfarin discontinuity. Also, an indicator variable of the discontinuity period will be added to the Cox's proportional hazards model.

Sensitivity analysis will be done to study the robustness of the discontinuity period definition.

Objective 3: The distribution of days taken to achieve INR target in the new warfarin user population will be provided. Stable INR-target is considered achieved after 3 consecutive INR measurements are within the target 2.0-3.0.

Objective 4: For the new warfarin user population the distribution of TTR at 1, 6, and 12 months after start of warfarin treatment stratified by other covariates. For the prevalent warfarin user population the distribution of TTR at the end of 2010 and 2011 stratified by other covariates.

Objective 5: Warfarin users will be tabulated by use of antiarrhythmic medication (yes/no) at start of follow-up and during follow-up. During follow-up users will also be stratified by the INR and the TTR levels.

Objective 6: Warfarin users will be tabulated by use of interaction medication (yes/no) at start of follow-up and during follow-up. During follow-up users will also be stratified by the INR and the TTR levels.

Objective 7: Warfarin users will be tabulated by comorbidities.

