2.3 Exploratory Objectives

- 1) To investigate and compare incidence of anemia and renal impairment among AF patients in relation to INR levels: under 2.0, 2.0-3.0, and over 3.0.
- 2) To investigate risk of stroke, systemic thromboembolic events, myocardial infarction, and bleeding events among AF patients in relation to discontinuation of warfarin treatment due to surgical operations and interventions.
- 3) To investigate how long it takes to achieve INR target in treatment initiators.
- 4) To investigate how well the INR target is maintained (TTR level).
- 5) To characterize the use of antiarrhythmic medication in AF patients at start of warfarin use and during warfarin use.
- 6) To characterize the use of medications with known interactions with warfarin in AF patients at start of warfarin use and during warfarin use.
- 7) To characterize comorbidity in AF patients using warfarin.

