3.3 Data Source/Data Collection Process

The study timelines are presented in the picture below:

Figure 3.3-1: Study Timelines

[figure not shown]

Table 3.3-1: Study Registers

Register	Register Holder	Information obtained
National Prescription Register	Kela – The Social Insurance Institution of Finland	Drug purchases (ATC codes)
National Reimbursement Register	Kela	Reimbursement decisions 207 for chronic arrhythmias (for population characterization)
Finnish Care Register, HILMO	National Institute for Health and Welfare	Diagnoses (ICD10 codes) and date of diagnosis
National Causes of Death Register	Statistics Finland	Time of death and causes of death (ICD-10 codes)
Laboratory databases	HUSLAB + other hospital laboratories	INR measurements and other relevant laboratory values
Finnish Cancer Registry	National Institute for Health and Welfare	Cancer diagnosis (ICD-O-3 codes) and date of diagnosis
Population Register	Population Register Center	Places of domicile 12 months prior to and on index dates.
Social HILMO	National Institute for Health and Welfare	Information (dates) about institutionalization (other than hospitalization)

- Data will be requested from the registry holders ([Table 3.3-1](#)) based on the study protocol.
- Data permits will be requested from each registry holder based on the study protocol and ethical approval.
- Approval of Ethical Review Board of Hospital District of Helsinki and Uusimaa (HUS) will be requested to cover the nationwide study.
- This is a fully register-based study and patients will not be contacted in any phase of the study.
- Warfarin exposure will be defined by Kela, who then will convert the patient IDs to study IDs (SIDs). Kela will then send the IDs and the SIDs to other register holders: Statistics Finland, National Institute for Health and Welfare, Statistics Finland, Population Register Center, and central hospital laboratories included in the study.
- EPID Research will receive unidentifiable data including SIDs only. All patient data handled by the researchers are then anonymous which ensures full data protection of the patients.

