3.4.3 Other Covariates/Control Variables

- Reimbursement code 207
 - Yes/no
- Information about hospitalizations and institutionalization (other than hospitalization)

- dates
- will be taken into account when defining the discontinuation of warfarin treatment
- Laboratory parameters for anemia characterizations
 - Blood picture
 - ◆ Haemoglobin
 - decrement of 20 g/L
 - being under the reference value
 - See [Appendix 2](#) for details.
- Concomitant use of class D interactive drugs according to SFINX (Swedish, Finnish, INteraction X-referencing, see [Appendix 3, Table 3](#) for complete ATC listing)
 - Concomitant use during the warfarin treatment period assumed by the purchases and exposure (see definition for exposure in Section 4.1).
- Age*
- Gender*
- Hospital district
 - Helsinki, Turku, Tampere, Kuopio, Oulu, Jyväskylä
 - other possible central hospitals
- CHADS₂^{11 12}
- CHA₂DS₂-VASc^{11,12}
- Comorbidities (more in detail in [Appendix 4](#))
 - Hypertension*
 - Thyrotoxicosis
 - Cardiomyopathy
 - Congestive heart failure*
 - Diabetes*
 - Stroke*
 - Transient ischemic attack*
 - Vascular disease**
 - Cancer
 - Venous thromboembolism
 - *included in CHADS₂ score and in CHA₂DS₂-VASc score
 - **included in CHA₂DS₂-VASc score.

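### Exploratory Objective 2 defines warfarin discontinuity by the procedure date alone, so its rates and Cox indicator describe the peri-procedural period, not interruption of warfarin

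*Protocol*

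**What the plan says.** Protocol Section 2.3 sets the question: risk of stroke, systemic thromboembolism, myocardial infarction and bleeding "in relation to discontinuation of warfarin treatment due to surgical operations and interventions". Section 4.1.3, Objective 2, then fixes the exposure. The period "is identified as starting two weeks before and ending two weeks after such procedure". Incidence rates are estimated "in the strata of other covariates within periods of warfarin discontinuity", and "an indicator variable of the discontinuity period will be added to the Cox's proportional hazards model". The only safeguard is one sentence: "Sensitivity analysis will be done to study the robustness of the discontinuity period definition". It names no alternative definitions.

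Other parts of the protocol bear on this:

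- Section 4.1.2, Objective 3, bases the end of treatment on observed data: "Warfarin treatment is considered ended if there is more than 2 months gap since last warfarin exposure and INR measurement". It names 1- and 3-month gaps as sensitivity analyses.
- Section 3.4.3 says that hospitalization and institutionalization dates "will be taken into account when defining the discontinuation of warfarin treatment", but nothing ties them to the 28-day rule.
- Table 3.3-1 lists "INR measurements and other relevant laboratory values" among the data to be obtained.
- Section 5 states that in-hospital medication is not observed and that some patients' laboratory values may be missing.

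**The concern.** The objective concerns interruption of warfarin. The rule records that a procedure took place. Followed as written, it has three effects.

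1. A patient who stayed on warfarin throughout contributes 28 days of discontinuity.
2. A patient who did stop contributes the days before the stop and after the restart as well.
3. The indicator marks the time around an operation, so bleeding or thromboembolism caused by the operation is credited to discontinuation. No separate term for the procedure is planned.

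In addition, the first 14 days are labelled by an event that has not yet happened, so pre-procedure time is classified with later information.

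At stake is whether a published rate or hazard ratio under the name of warfarin discontinuity means what it says. A reader could not correct it, because neither the share of uninterrupted time nor the procedure's own effect is identified.

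**Working it through.** **Figure to reproduce.** None. The protocol gives no rate, effect size or power for this objective. Table 4.2-1 concerns a different comparison.

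**Input from the protocol.** The window is 14 + 14 = 28 days, or 28 / 365.25 = 0.077 person-years per procedure.

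**Assumed inputs, none given in the protocol.**

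- HR, the true hazard ratio for being off versus on warfarin: mainly 2.0, with 3.0 as a second case.
- p, the share of window time truly off warfarin: 0.25, 0.50, 0.75. For scale, if every patient stopped for 7 to 14 days, p would be 7/28 = 0.25 to 14/28 = 0.50.
- s, the procedure's own hazard ratio: 1, 1.5, 2.

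**Formula.** With constant rates, a reference of procedure-free time on warfarin, and no INR term in the model:

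window HR = s × (p × HR + 1 − p)

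The window HR equals the true HR when s = HR / (p × HR + 1 − p). Above that value of s it overstates the effect, and below it understates it.

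**Results for true HR = 2.0.**

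| p | s = 1 | s = 1.5 | s = 2 | break-even s |
|---|---|---|---|---|
| 0.25 | 1.25 | 1.88 | 2.50 | 1.60 |
| 0.50 | 1.50 | 2.25 | 3.00 | 1.33 |
| 0.75 | 1.75 | 2.62 | 3.50 | 1.14 |

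For example, at p = 0.50 the bracket is 0.5 × 2.0 + 0.5 = 1.5. Multiplying by s gives 1.50, 2.25 and 3.00, and the break-even is 2.0 / 1.5 = 1.33. For true HR = 3.0 and p = 0.50 the bracket is 2.0, so s = 1 gives 2.00, s = 2 gives 4.00, and the break-even is 1.50.

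**Bleeding.** Being off warfarin may lower the bleeding hazard. Taking the mirror image of 2.0, HR = 1 / 2.0 = 0.5 (assumed), with p = 0.50, the bracket is 0.5 × 0.5 + 0.5 = 0.75. With s = 1 the window shows 0.75. With s = 2 it shows 1.50, the opposite sign from the truth. The bias may therefore differ by endpoint.

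**If the Cox model also contains INR.** Section 4.1.3 does not say which Cox model receives the indicator. The models elsewhere in Section 4.1 are fitted by INR level and, separately, by TTR category. If the INR model is meant, the formula above does not describe the coefficient. The indicator then compares window and non-window time at the same INR level. It is conditioned on the main marker of interruption and moves further from the question in Section 2.3.

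**The case against.** **A fixed window is a reasonable proxy.** In-hospital drug use is unobserved, and purchase-based exposure is lengthened by a factor of 1.5 in Section 4.1, so it is poorly suited to showing a short stop. This supports using a window. It does not support calling it discontinuity.

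**The detail belongs in the SAP.** Section 4.1 promises one, and Section 4.1.3 promises a sensitivity analysis. Procedure lists and alternative definitions are fair SAP content. The main rule, however, is fixed in the protocol, and varying the window width alone would never show whether warfarin was stopped.

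**The rule covers only discontinuity due to a procedure.** That wording could be read as limiting it to procedures with a stop, but no criterion applies the limit.

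**INR cannot prove a stop.** This stands. Section 4.2 cites 21.7% of routine INR measurements below 2.0, so a low value does not establish interruption. Equally, two in-range values a week apart do not prove that warfarin was never stopped. Requiring an INR taken after the procedure would also admit only patients who survived to be tested, and testing may be prompted by the event. These points shape the remedy. They do not rescue the present rule.

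**A stronger reading.** A reader might infer that misclassification dilutes the effect, so the estimate is at least conservative. That holds only for s = 1. The same indicator carries the procedure's own risk, and the protocol gives nothing to fix the net direction.

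**Conclusion.** The point holds. The exposure is set by procedure timing alone, and its rates and Cox indicator describe a peri-procedural period rather than interruption of warfarin. Neither the unspecified sensitivity analysis nor the general statement on hospitalization dates repairs this.

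The size cannot be stated from the protocol. Over the assumed ranges, a true hazard ratio of 2.0 could appear anywhere from 1.25 to 3.50. That range shows that the estimate can err in either direction and does not forecast its value. It rests on assumed p and s, constant rates, and a model without INR.

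The protocol supports no claim that the effect is diluted, and none about how many patients continue warfarin. The consequence is confined to one exploratory objective. Primary and secondary results do not depend on it.

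**What to change.** 1. Rename the 28-day exposure the peri-procedural period, and report time before and after the procedure separately.
2. State whether the Cox model that receives the indicator also contains INR level, and interpret the coefficient accordingly.
3. Give the promised sensitivity analysis its content: split peri-procedural time by the most recent INR recorded up to that day within the window. The classes are below 2.0 after an earlier in-range value, 2.0 or above, and no INR (unknown). A low INR with no earlier in-range value can join the unknown class. Update the class over time, so that no later INR classifies earlier days. This calls for the last recorded value and not the interpolated one in Section 4.1, which uses the next measurement. Say how an INR taken on the day of an event is handled, since the event may have prompted it.
4. Compare the below-2.0 class with the 2.0-or-above class, both within the window, and draw conclusions about interruption only from that contrast. State that INR is a proxy for stopping.

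The cost is wording and programming on data already planned for collection. The price is fewer events per stratum and an unknown group that may be selective, so its size and event rates should be shown.
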